During the treatment period (baseline/day of randomization [DoR, V3] through week 16 [V9]), patients will perform morning lung function assessments (FEV₁ and PEF) by handheld device prior to morning asthma maintenance medication and prior to rescue medication use (whenever possible), assess and record daytime and night-time asthma symptom scores, record rescue medication use (number of puffs) twice daily and confirm (in the evening) that they have taken that day's asthma maintenance medication. During the treatment period visits, formal pulmonary function testing (as required) will be completed in the morning between 0530 and 1100±1 hour on the study-provided spirometry equipment. If a patient has taken rescue medication within 6 hours of the planned pulmonary function testing or has taken the morning dose of asthma maintenance medication, the testing should be cancelled, and the visit should be rescheduled. All formal pulmonary function testing should be conducted at approximately the same time of day ±1 hour of the time it was conducted at baseline/DoR (V3). Other procedures for each visit are outlined in [Table 2](#).

Patients who complete week 16 (end of treatment visit [EoTV; V9]) will enter the follow-up period. The handheld device and diary, along with study provided rescue medication will be collected. The investigator should determine and implement appropriate asthma therapy (including rescue treatment) to be used during the follow-up period. Medication started for the purpose of ongoing asthma treatment will not be considered a protocol violation, provided it is started after the final spirometry assessments are completed at week 16 (V9). Patients will be contacted approximately monthly by telephone to assess CAEs, adverse events, and concomitant medications. A final follow-up visit will occur at approximately week 30 for final assessments. A CAE is defined as worsening asthma requiring treatment with a systemic corticosteroid for ≥3 days, emergency room visit resulting in systemic corticosteroid treatment or hospitalization due to asthma. All instances of a CAE should be recorded in the CRF.

Alert criteria for individual patients who develop worsening asthma have been designed to ensure patient safety. If any of the criteria listed below are met, the investigator will determine whether the patient's overall clinical picture is consistent with worsening asthma and if the

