4.1. Patient Inclusion Criteria

Patients may be included in this study only if they meet all of the following criteria:

- a. The patient is capable of giving signed informed consent.
- b. The patient is an adult female or male ≥ 18 years of age. Note: Age requirements are as specified or allowed by local regulations.
- c. [Revision 1] The patient has a diagnosis of asthma for at least 6 months as defined by the National Institutes of Health (NIH) and has been stable without exacerbation or change in medications for at least 1 month.
- d. The patient has an absolute blood eosinophil count ≥ 300 cells/ μ L demonstrated during the screening period. Note: Rounding of the value (count) is not permitted.
- e. Severity of Disease: The patient has persistent asthma, with a trough FEV₁ $\geq 40\%$ and $\leq 85\%$ of the value predicted as per the National Health and Nutrition Examination Survey (Hankinson et al 1999, NHANES III 1998) and adjusted for ethnicity (Hankinson et al 2010). Note: Patients who do not qualify for the study due to failure to meet baseline spirometry or fail to achieve spirometry consistent with the American Thoracic Society (ATS)/European Respiratory Society (ERS) criteria (Miller et al 2005) will be permitted to perform repeat spirometry during the screening period on 1 occasion and if criteria are not met, will be considered to have failed screening.
- f. Reversibility of Disease: The patient has demonstrated reversibility of $\geq 12\%$ (increase) of FEV₁ and a minimum 200 mL increase from pre-albuterol/salbutamol FEV₁ approximately 30 minutes after 4 inhalations of albuterol/salbutamol hydrofluoroalkane (HFA) metered-dose inhaler (MDI) (90 μ g ex-actuator) or equivalent during the screening period.
- g. [Revision 1] Current Asthma Therapy: The patient has been maintained for at least 1 month on stable doses of:
 - medium or high dose ICS+another controller.
 - any fixed dose combination ICS (low, medium, or high) with LABA+another controller.
- h. Women of non-childbearing potential who are either surgically (documented hysterectomy, bilateral oophorectomy, or bilateral salpingectomy) or congenitally sterile as assessed by a physician, or 1-year postmenopausal (no menses for at least 12 months without an alternative medical cause plus an increased concentration of follicle stimulating hormone [FSH] of more than 35 U/L in women not using hormonal contraception or hormonal replacement therapy). Women of childbearing

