- h. The patient has complied with home spirometry and diary entry on at least 5 of the last 7 days prior to the visit including:
 - completion of daytime and night-time asthma symptom scores
 - completion of daytime and night-time rescue medication use, whether used or not
 - completion of the morning FEV₁ and PEF by handheld device
 - confirmed daily use of asthma maintenance medication as prescribed
- i. The patient has not had an upper respiratory infection (URI) or lower respiratory infection (LRI) during the run-in period. Patients who develop a URI or LRI during the run-in period may be discontinued from the study and allowed to rescreen 2 weeks after resolution of symptoms. They must have a negative test for COVID-19 active infection.
- j. The patient has used rescue medication or had a daytime or night-time asthma symptom score ≥ 1 on 3 or more days in the 7 days prior to the randomization visit as reported in the patient diary.

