5.7. Prior and Concomitant Medication or Therapy

Any prior or concomitant therapy, medication (including prior asthma medication), or procedure a patient has had from 30 days before screening through the end of the study will be recorded in the source documentation and in the CRF. Trade name and INN (if available), indication, dose, and start and end dates of the administered medication or treatment will be recorded. The sponsor will encode all therapy and medication according to the World Health Organization drug dictionary (WHO Drug).

Prohibited and restricted medications are listed in [Appendix G](#).

At each visit at the investigational center after the screening visit, the investigator will ask patients whether they have had any change in maintenance medication (including asthma maintenance medication), taken any other medications, including over-the-counter medications, vitamins, or herbal or nutritional supplements, since the previous visit.

Concomitant medication and treatment will be recorded until the follow-up visit.

For details of the management of study activities during COVID-19 outbreaks, see [Appendix N](#).

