2. STUDY DESIGN

2.1. General Design

This is a multicenter, randomized, double-blind, placebo-controlled, parallel-group study to evaluate the safety and efficacy of TEV-53275 administered subcutaneously (sc) at doses of 600 mg and 1200 mg or placebo in adult patients with moderate to severe asthma with an eosinophilic phenotype.

Patients may be eligible to participate if they have a diagnosis of asthma for at least 6 months and their current asthma maintenance therapy has been stable for at least 1 month and includes 1 of the following (see Appendix F in the study protocol):

- medium or high dose inhaled corticosteroid (ICS)±another controller
- any fixed dose combination ICS (low, medium or high) with a long-acting β -adrenergic agonist (LABA)±another controller

The patient will continue on this asthma maintenance therapy throughout the treatment period [V9/end of treatment visit (EoTV)]. For patients taking once-daily inhaled treatment, it must be taken in the morning to enable trough lung function assessments. If a patient requires a change in the timing of dosing, it is allowable as long as the investigator believes there is no inherent harm in changing the timing of the dose and the patient agrees to such change.

The study will consist of 4 periods:

- screening period of up to approximately 2 weeks
- run-in period of approximately 14 days
- double-blind treatment period of 16 weeks
- follow-up period of approximately 14 weeks beginning at the end of the double-blind treatment period

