4.2. Specification of Baseline Values

Unless otherwise specified, baseline value is defined as the last observed value before the administration of IMP.

The baseline for hand-held spirometry parameters and e-diary variables will be the average of the values over the 7 days preceding day of randomization.

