6.3. Secondary Efficacy Endpoints and Analyses

The key secondary efficacy endpoints are listed in Section 1.1. Analyses will be based on the mITT analysis set.

6.3.1. Overall Weekly Well-Controlled Asthma Status Defined by the Asthma Control Composite Score and Weekly Asthma Control Status (Yes Versus No) From Week 1 Through 12 and Overall Weekly Well-Controlled Asthma Status From Week 1 Through 16

The weekly asthma control status (Yes or No) is the derived asthma control composite score based on the following criteria (also see Section 6.1.7 of the study protocol):

1. Two or more of the following criteria are fulfilled
 - ≤ 2 days with a daily asthma symptom score >1
 - ≤ 2 days of albuterol/salbutamol used as rescue medication up to a maximum of 4 occasions per week (multiple occasions per day are counted as separate occasions)
 - morning FEV₁ $\geq 80\%$ predicted for each day (by handheld device)

and

[figure not shown]
2. Both of the following criteria are fulfilled:
 - no night-time awakenings due to asthma
 - no use of asthma maintenance medications

For the analysis purpose, weekly analysis windows (weeks 1 to 16) will be derived as described in Section 6.1.1. The asthma control status in each weekly analysis window will be Yes if the conditions 1 and 2 above met, No otherwise.

The overall weekly asthma control status from week 1 through 12 or week 1 through 16 will be analyzed using the repeated measures logistic regression with treatment group, baseline status, and the randomization stratification factor, week, and week-by-treatment group interactions in the model and with the unstructured (UN) covariance structure. In the case UN covariance structure does not converge, the compound symmetry covariance structure (CS) will be used. All weekly asthma control statuses from weeks 1 to 16 will be included in the repeated measures model.

To estimate the probability of overall asthma control over 12 weeks in each treatment group, or to conduct a comparison between the treatment groups, appropriate contrast statements need to be used.

6.3.2. Overall Changes From Baseline in the Weekly Average of Daily Morning Trough (Pre-Rescue Bronchodilator) FEV₁ as Measured by a Handheld Device Over 12 Weeks From Week 1 Through 12 and Over 16 Weeks From Week 1 Through 16

[figure not shown]

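### Read literally, the weekly asthma control composite scores No in every week with background maintenance use, which the trial requires of all patients

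*SAP*

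**What the plan says.** SAP 6.3.1 derives a Yes/No control status for each of weeks 1 to 16. A week is Yes only if two conditions both hold, and otherwise No. Condition 1 asks for at least two of three items on symptoms, rescue use and home FEV₁. Condition 2 requires both of its items: no night-time awakenings due to asthma, and "no use of asthma maintenance medications". Protocol 6.1.7 words the second item identically.

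The same documents make maintenance therapy compulsory:

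- Inclusion criterion g (protocol 4.1): "The patient has been maintained for at least 1 month on stable doses of" inhaled corticosteroid, or of a fixed combination with a long-acting beta-agonist.
- SAP 2.1: "The patient will continue on this asthma maintenance therapy throughout the treatment period", that is, to V9 at week 16.
- Protocol 3.1: in the treatment period patients "confirm (in the evening) that they have taken that day's asthma maintenance medication".
- Randomization criterion h (protocol 4.3): "The patient has complied with home spirometry and diary entry on at least 5 of the last 7 days prior to the visit including", among other entries, "confirmed daily use of asthma maintenance medication as prescribed".

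SAP 4.2 sets the baseline for e-diary variables as the "average of the values over the 7 days preceding day of randomization". SAP 6.3.1 puts baseline status, randomization stratum, week, treatment and week-by-treatment interaction into a repeated-measures logistic model. The covariance is unstructured, with compound symmetry as fallback.

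**The concern.** The item contradicts the design. A patient who follows the protocol uses maintenance medication every day and so fails condition 2 every week, whatever the treatment does. The few weeks that could pass would be weeks in which background therapy was not taken at all, which is not asthma control.

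This is the first-listed secondary efficacy endpoint. It is also repeated across the five subgroup variables in SAP 6.2.3. Literal programming leaves a model with almost no events and a constant baseline covariate. Programming by inference makes the derivation an undocumented choice on points that can change week-level results.

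**Working it through.** The plan states no figure for this endpoint, so there is none to reproduce. The check is logical, followed by a count of how many weeks could be Yes.

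**Post-baseline logic.** Yes requires condition 1 and condition 2. Condition 2 requires zero maintenance use in the 7-day window. Zero use is therefore necessary for Yes, though not sufficient.

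**Baseline logic.** Criterion h needs confirmed use on at least 5 of 7 days, which leaves at most 7 − 5 = 2 days without confirmed use. Yes needs 7 such days. Taking the baseline week as the 7 days before randomization, every patient who meets criterion h is No.

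**Number of patient-weeks.** Inputs are 300 patients (protocol 3.2), reduced totals of 270 or 240 (SAP 13.1.3), 1:1:1 allocation, 16 weeks, and dropout of 15% on placebo and 8% on each active arm (protocol 9.1). The lower figures assume that all dropouts leave before week 1.

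| Randomized | Dropout | Patient-weeks |
|---|---|---|
| 300 | none | 300 × 16 = 4,800 |
| 300 | 15% / 8% / 8% | (85 + 92 + 92) × 16 = 4,304 |
| 270 | 15% / 8% / 8% | (76.5 + 82.8 + 82.8) × 16 = 3,874 |
| 240 | 15% / 8% / 8% | (68 + 73.6 + 73.6) × 16 = 3,443 |

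**Weeks that could qualify.** The documents give no rate of complete non-adherence, so it is assumed.

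| Assumed share of zero-use weeks | Of 4,800 | Of 3,443 |
|---|---|---|
| 0% | 0 | 0 |
| 0.5% | 24 | 17 |
| 1% | 48 | 34 |

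There are 3 arms × 16 weeks = 48 cells, so the 1% case gives at most 48 / 48 = 1.0 week per cell before the awakening item and condition 1 are applied.

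**A second way to assume it.** If daily adherence is p and days are independent, P(zero use in 7 days) = (1 − p)^7.

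| Daily adherence p | P(zero-use week) | Expected in 4,800 |
|---|---|---|
| 90% | 0.0000001 | 0.0005 |
| 80% | 0.0000128 | 0.06 |
| 70% | 0.00022 | 1.0 |
| 50% | 0.0078 | 37.5 |
| 30% | 0.082 | 395 |

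Appreciable numbers appear only when adherence is very poor, and those weeks would reflect abandoned background therapy.

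**Data source.** The text does not say which record feeds the item. The daily diary confirmation (protocol 3.1) shows whether a dose was taken. The medication record covers "Any prior or concomitant therapy, medication (including prior asthma medication), or procedure a patient has had from 30 days before screening" to the end of the study, with start and end dates (protocol 5.7). A patient with an open-ended background entry there would be No even in a week when every dose was skipped. Zero use remains necessary under either source, but the two can classify the same week differently. No rule is given for days with a missing confirmation, which careless code could count as no use.

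**The case against.** The best reply is that the sponsor plainly meant added medication. The intercurrent-event text (protocol 9.5.4.1, SAP 1.3.1) uses almost the same phrase for the observations to be excluded. Read literally there, it would remove every post-baseline FEV₁ value. On that view this is a missing qualifier in one of twelve secondary endpoints, in a phase 2 trial with no multiplicity control.

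That is probably the intent. But the estimand text first describes patients placed on systemic corticosteroids or additional therapy for worsening asthma, and this fixes the meaning. It is also why the primary analysis is unaffected. The composite definitions have no such lead-in. Protocol 6.1.2 speaks of addition when it means addition, and SAP section 15 lists no correction. Inferring the qualifier also leaves open whether a dose increase counts, and whether systemic corticosteroids count: protocol 6.1.2 separates them from maintenance medication, while the estimand text groups them with added therapy.

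Three further points stand in part:

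- SAP 4.2 describes an average and gives no explicit rule for a binary baseline, so using the same 7 days is an inference.
- Baseline would be mostly No even with the item corrected. Criterion b in protocol 4.3 caps average home FEV₁ at 80% predicted, and criteria e and j require uncontrolled or symptomatic asthma. The correction restores Yes weeks after baseline but may not give the covariate much variation.
- The 0% to 1% share is assumed, so 48 weeks is not a strict bound. The patient-week range also excludes a stop for futility.

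**Conclusion.** The definition is wrong as written. It makes the endpoint incompatible with the therapy that every patient must take. With literal coding, 100% of patients meeting criterion h are No at baseline. After baseline about 0 to 48 of 3,443 to 4,800 patient-weeks could be Yes, if up to 1% of weeks have no maintenance use at all. Odds ratios and control probabilities from the planned model could not be estimated, and compound symmetry does not cure an absence of events. With coding by inference the model may run, but on an unspecified derivation. The subgroup analyses of this endpoint share the fault. The primary endpoint, its estimand, its power and the interim rules do not. This should be fixed, but it does not threaten the main conclusion of the trial.

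**What to change.** Before unblinding, amend the item in SAP 6.3.1 as follows:

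- Limit it to asthma maintenance medication added to the background regimen in use at randomization.
- State whether an increase in dose of the background regimen counts, and whether systemic corticosteroids count.
- Name the source, either the diary confirmation or the concomitant medication record, and give the rule for missing entries.
- Define baseline status by the same rule over a stated window. Check on blinded data whether it varies enough to keep as a covariate.

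The cost is a few lines of text, because both data sources are already collected. The SAP introduction says the SAP prevails over the protocol, so the SAP edit is enough to govern the analysis, with the difference explained in the study report. Protocol 6.1.7 should be brought into line as well. Since Appendix C generally requires ethics approval for amendments, that change can go with the next amendment.

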5.8. Procedures for Monitoring Patient Compliance

The investigator will be responsible for monitoring patient compliance with this protocol from the start of the screening/run-in period through the follow-up visit. If the investigator or the sponsor determines that the patient is not in compliance with the study protocol, the investigator and the sponsor should determine whether the patient should be withdrawn from the study. The Independent Ethics Committee/Institutional Review Board (IEC/IRB) should be notified if

required by local regulation. Compliance with the patient diary will be deemed adequate if 80% of the data is captured through V9.

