6.1.7. Asthma Control Composite Score

The weekly asthma control composite score will be based on the following, modified from [O'Byrne et al \(2018\)](#) to include daily morning FEV₁ instead of PEF:

1. Two or more of the following criteria are fulfilled
 - ≤ 2 days with a daily asthma symptom score >1
 - ≤ 2 days of albuterol/salbutamol used as rescue medication up to a maximum of 4 occasions per week (multiple occasions per day are counted as separate occasions)
 - morning FEV₁ $\geq 80\%$ predicted for each day (by handheld device)

And

2. Both of the following criteria are fulfilled:

- no night-time awakenings due to asthma
- no use of asthma maintenance medications

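### SAP 6.3.1 scores weekly asthma control from fixed counts of recorded bad days, with no minimum number of diary days, so incomplete weeks are pushed towards Yes

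*SAP*

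**What the plan says.** SAP 6.3.1 builds the weekly status from two conditions.

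- Condition 1 needs at least two of three elements. The first limits symptoms: "≤ 2 days with a daily asthma symptom score >1". The second limits reliever use to at most 2 days and at most 4 occasions in the week, with repeat occasions on one day counted separately. The third is handheld morning FEV₁ of at least 80% predicted on each day.
- Condition 2 needs both "no night-time awakenings due to asthma" and that no maintenance medication for asthma was used.

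The outcome is then two-way: "The asthma control status in each weekly analysis window will be Yes if the conditions 1 and 2 above met, No otherwise". All statuses from weeks 1 to 16 enter the repeated-measures logistic model. Protocol 6.1.7 lists the same elements and has no diary minimum either.

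Three general rules bear on incomplete weeks. SAP 4.3 uses observed data only and estimates nothing unless specified, and nothing is specified for 6.3.1. SAP 6.1.1 accepts a last window shorter than 7 days for early withdrawals. Protocol 6.1.6 lets the site's inhaler-counter tracking stand in for missing diary rescue data.

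Two diary standards exist. Protocol 5.8 sets one for the treatment period as a whole: "Compliance with the patient diary will be deemed adequate if 80% of the data is captured through V9". Protocol 4.3 sets one per week, but only for entry: "The patient has complied with home spirometry and diary entry on at least 5 of the last 7 days prior to the visit".

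Other endpoints handle incompleteness explicitly. SAP 6.3.3 and 6.3.4 divide by non-missing e-diary days, and SAP 6.3.9 to 6.3.11 give rules for incomplete questionnaires.

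**The concern.** The symptom, rescue and awakening elements are ceilings on what was recorded. Removing a day from the record can lower a count but never raise it, so missing entries move these elements in one direction, towards Yes. The FEV₁ element is different in kind, but only two of the three condition 1 elements are needed, so the two day-counts are enough. Patients also enter with average handheld FEV₁ of 40% to 80% predicted (Protocol 4.3), so for many of them the day-counts will decide condition 1.

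This is the first-listed secondary efficacy endpoint and one of the endpoints selected for subgroup analysis (SAP 6.2.3). If diary completeness differs between arms, part of the odds ratio reflects adherence rather than control. The sponsor's own sample-size simulations assume 15% dropout on placebo and 8% on each active arm, so unequal completeness is plausible. Even equal incompleteness changes the control rates and the odds ratio.

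**Working it through.** The documents give no expected control rate or power for this endpoint, so there is no stated figure to reproduce. The 80.6% power in SAP 2.4 concerns FEV₁ and is unaffected.

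**1. What the study-wide standard permits.** 16 weeks is 112 diary days, and 20% of 112 is 22.4. So 22 days may be missing, about three whole weeks, with compliance still adequate.

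**2. Chance of Yes by number of diary days.** Inputs from SAP 6.3.1: limits of 2 symptom days, 2 rescue days and 0 awakenings. Assumptions, not in the documents:

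- daily rates s (symptom score above 1), r (rescue use) and w (awakening)
- independence between days and between elements
- one rescue occasion per rescue day, so the 4-occasion cap does not bind
- FEV₁ element not met, maintenance-medication element met

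With m observed days,

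P(Yes) = P(Bin(m, s) ≤ 2) × P(Bin(m, r) ≤ 2) × (1 − w)^m.

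For s = r = 0.4, w = 0.05:

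- m = 7: 0.4199² × 0.95⁷ = 0.1763 × 0.6983 = 12.3%
- m = 5: 0.6826² × 0.95⁵ = 0.4659 × 0.7738 = 36.0%
- m = 3: 0.9360² × 0.95³ = 0.8761 × 0.8574 = 75.1%
- m = 2: 1 × 1 × 0.95² = 90.3%

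Other assumed rates, for m = 7, 5, 3, 2:

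| s = r | w | 7 | 5 | 3 | 2 |
|---|---|---|---|---|---|
| 0.2 | 0.02 | 63% | 80% | 93% | 96% |
| 0.6 | 0.05 | 0.6% | 8% | 53% | 90% |

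**3. Averaged over random missingness.** Let each day be missing independently with probability 0.2, and average P(Yes) over m ~ Bin(7, 0.8). The 5-of-7 column averages over m = 5, 6, 7 only.

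| s = r, w | Complete week | Literal count | 5-of-7 minimum |
|---|---|---|---|
| 0.2, 0.02 | 63.0% | 74.8% | 72.4% |
| 0.4, 0.05 | 12.3% | 29.4% | 24.1% |
| 0.6, 0.05 | 0.6% | 7.7% | 3.7% |

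Equal missingness does not cancel. The odds ratio between the first two rows is (0.630/0.370)/(0.123/0.877) ≈ 12 on complete weeks and (0.748/0.252)/(0.294/0.706) ≈ 7 on the literal count.

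**4. Blank weeks.** With 3 of 16 weeks blank and s = r = 0.4, w = 0.05, the control rate is (13 × 0.123 + 3)/16 = 28.8% if blank is Yes, 13 × 0.123/16 = 10.0% if No, and 12.3% if missing. The plan does not choose among these.

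**5. Effect of prorating.** Scaling to 7 days requires count × 7/5 ≤ 2 or count × 7/6 ≤ 2, so at most 1 bad day in either case. At s = r = 0.4, w = 0.05:

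- m = 5: 0.3370² × 0.95⁵ = 8.8%
- m = 6: 0.2333² × 0.95⁶ = 4.0%

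Weighting m = 7, 6, 5 by 0.2097, 0.3670 and 0.2753 (sum 0.8520) gives (0.2097 × 0.123 + 0.3670 × 0.040 + 0.2753 × 0.088)/0.8520 = 7.6%, against 12.3% for complete weeks. Prorating therefore errs towards No.

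**The case against.** A reader might infer that the plan classes any week with missing entries as well controlled by default. It does not. The residual category in the quoted sentence is No, and no passage states that a missing day is a good day. That follows only from applying fixed counts to observed data. A week with any recorded awakening is No however sparse it is. A blank week could be read as Yes by counting, as No because the conditions cannot be shown to hold, or as missing under SAP 4.3.

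A reader might also infer that a week with 2 or fewer diary days passes both day-count elements automatically. Only the symptom element does. The rescue element also caps use at 4 occasions, so three occasions on each of two days fail it, and the inhaler counter may recover some unrecorded use.

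The size is also uncertain. The daily rates are assumed, days with a symptom score of only 1 do not count as bad, and the documents give no adherence data. Diary compliance is reviewed at clinic visits and 80% capture is expected, so very sparse weeks may be uncommon. The success and sample-size rules rest on clinic FEV₁, not this endpoint.

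All of this stands and limits the claim. It does not supply the missing rule: the 80% standard is not applied per week, and the 5-of-7 standard stops at randomization.

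**Conclusion.** The point holds in limited form. SAP 6.3.1 has no diary minimum, scaling or missing status, and its counts applied to observed data push incomplete weeks towards Yes. This is more than absent detail, because following the text as written shifts the result, and the neighbouring diary endpoints in SAP 6.3.3 and 6.3.4 avoid the problem with a non-missing denominator.

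For the middle set of assumed rates, 20% random missingness lifts the control rate from 12.3% to 29.4%. Across the three sets examined the rise runs from about 7 to 17 percentage points. These figures rest on independent days, randomly missing entries and the other assumptions listed; they illustrate the mechanism and do not forecast this trial. The direction of any bias between arms cannot be determined from the documents. It depends on which arm has more incomplete weeks and how blank weeks are read. The primary endpoint and the interim rules are untouched.

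**What to change.** Amend SAP 6.3.1 before unblinding:

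1. Derive the weekly status only when at least 5 of the 7 days have complete diary data, the standard the protocol already applies at randomization. Set all other weeks to missing, including blank weeks and short final windows.
2. Because a 5-of-7 minimum alone leaves much of the inflation (29.4% falls only to 24.1%, against 12.3%), prorate the day and occasion counts to 7 days in weeks with 5 or 6 observed days, or add a sensitivity analysis restricted to complete weeks.
3. Add a sensitivity analysis scoring incomplete weeks as No.

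The change is SAP wording and programming; no new data are needed. The main cost is more missing weeks, which may not be missing at random if patients skip the diary when unwell. Under 20% random missingness, 14.8% of weeks would fall below 5 days (1 − 0.852), and only 21% (0.8⁷) would be complete, so a complete-weeks analysis would be imprecise. Prorating overcorrects somewhat, because it tightens the limit from 2 bad days to 1.

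While editing, reconcile the element requiring no use of maintenance medication with SAP 2.1, under which patients continue maintenance therapy throughout treatment. Read literally, it would make every such week No.
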